13.7.1.2.2 Data transformation before analysis, if any

No data transformation will be applied to raw data.

13.7.1.2.3 Main statistical model and adjustment for covariates

For the primary analysis, all adjudicated events occurring from randomization to the study end date (inclusive) will be counted, including events occurring after early permanent discontinuation of study drug. The proportion of patients remaining event-free over time will be displayed in the form of survival curves using the Kaplan-Meier method and analyzed (primary analysis) using a two-sided log-rank test. Statistical significance will be claimed if the computed p-value is equal to or less than 0.05.

The number and percentage (crude rate) of patients experiencing a primary endpoint will be summarized.

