8.3 Method of assigning patients to treatment group

The Interactive Voice Response System (IVRS) center will allocate treatment based on a pre-specified randomization list, generated by the IVRS provider, using study center as stratification parameter. A list of treatment kit numbers for each treatment group is generated centrally by sanofi-aventis and the treatment kits are prepared in accordance with this list. Numbers will not be reused regardless of the status of the use of the corresponding study drug.

After the patient signs the informed consent, and after eligibility is documented based on inclusion/exclusion criteria, the Investigator will call the IVRS center to receive the number for that treatment kit and the subject number to be allocated to the patient. Patients will be considered randomized as soon as the first allocation of treatment kit number is given as documented by the IVRS center.

All patients who are allocated a treatment kit number (ie, randomized) by the IVRS are irrevocably in the study, whether or not they are subsequently found to be eligible or actually receive the allocated treatment, and they should be followed until the End of Study visit or death, whichever comes first.

The first study drug intake should take place as soon as possible after randomization (on the same day), under medical supervision. If patients temporarily discontinue study medication, they should resume taking it as soon as possible.

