13.2 Determination of sample size

Based on the targeted population for the study, 3% is considered a reasonable assumption for the yearly event rate in the placebo group. Assuming recruitment over a 17 month period, and a total study duration of 50 months, 8,500 patients per group (total 17,000) will give a power of 90% (two-sided test, at the 5% significance level) to the trial to show an overall 15% risk reduction (or equivalently no effect the first year, followed by a 25% risk reduction in subsequent years). This corresponds to approximately 1,600 events.

These computations allow for a 10% annual rate of treatment discontinuation.

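### The primary log-rank test is valid and sufficient, but as written it uses no prognostic stratum; stratifying by entry category, and optionally by pooled country, would add a little power

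*Protocol*

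**What the plan says.** Protocol section 13.7.1.2.3 covers the main model and covariate adjustment. Time to first adjudicated event is to be shown by Kaplan-Meier curves and "analyzed (primary analysis) using a two-sided log-rank test". It adds: "Statistical significance will be claimed if the computed p-value is equal to or less than 0.05". It names no stratum and no covariate, and it does not use the word unstratified. The synopsis likewise gives a log-rank comparison of two groups at the two-sided 0.05 level.

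Randomization (section 8.3) is done centrally "using study center as stratification parameter"; no other factor is named. The synopsis expects about 600 active sites.

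Under section 7.2 a patient enters either with at least one CHD risk equivalent or with two major cardiovascular risk factors. Section 12.1.2 has compliance with these criteria checked and recorded in the CRF. Section 13.3.1 tabulates randomized patients by country, so country is on file too. Neither item enters the primary test. Age, gender and race appear only in the Cox subgroup models of section 13.7.1.2.5.

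Section 13.2 states that "8,500 patients per group (total 17,000) will give a power of 90% (two-sided test, at the 5% significance level") for a 15% risk reduction, and "This corresponds to approximately 1,600 events". Section 13.7.2.2 carries the same method to the secondary composite and to all-cause mortality. Section 13.1 calls this material the basis for a later statistical analysis plan, which is not at hand.

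**The concern.** When patients with unequal event rates are pooled, the marginal hazard ratio sits slightly closer to 1 than the ratio within risk groups, and the log-rank statistic shrinks with it. A test stratified on a prognostic factor avoids this at almost no cost in information, provided the strata are coarse.

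The protocol itself expects risk to differ by entry route. Section 4.3 separates moderate-risk from high-risk patients, and separates symptomatic disease or diabetes from combinations of other risk factors. In a worldwide trial, event rates may also differ by country.

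What is at stake is a little power, from data already collected, in a trial whose planned event count is close to the minimum for its target. The same choice carries through to the secondary endpoints in the hierarchy.

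**Working it through.** **1. The plan's own figure.** Inputs from section 13.2: hazard ratio 0.85 (constant 15% reduction), two-sided 5%, 90% power, 1:1 allocation. (z₀.₉₇₅ + z₀.₉₀)² = (1.960 + 1.282)² = 10.507, and (ln 0.85)² = 0.02641.

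- Schoenfeld: 4 × 10.507 / 0.02641 = 1,592 events.
- Freedman: (1.85/0.15)² × 10.507 = 152.11 × 10.507 = 1,599 events.
- Power at 1,600 events: Φ(√(1,600/4) × 0.1625 − 1.960) = Φ(1.290) = 90.2%.

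The stated 1,600 reproduces with an ordinary log-rank test.

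**2. Events the schedule yields.** Section 13.2: "3% is considered a reasonable assumption for the yearly event rate in the placebo group" and "Assuming recruitment over a 17 month period, and a total study duration of 50 months". Taking 3% as the one-year risk, the placebo hazard is 0.03046 per year and the treated hazard 0.85 times that. Uniform accrual gives follow-up of 33 to 50 months. The expected event proportions are 9.99% and 8.56%, so 8,500 × (0.0999 + 0.0856) ≈ 1,577 events and Φ(√(1,577/4) × 0.1625 − 1.960) = 89.7% power. The delayed-effect variant and the allowance for discontinuation in section 13.2 are not examined here.

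**3. Gain from stratifying by risk group, and by center.** Simulation: 17,000 patients, 600 centers, permuted blocks of 4 within center, hazard ratio 0.85, 1,000 trials per row, all tests applied to the same data. With k the ratio of mean Z to the unstratified mean Z, power from a 90% base is Φ(3.2415k − 1.960). The group sizes, relative hazards, center spread and block size are assumptions.

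| Assumed groups (equal sizes, relative hazards) | SD of center log-hazard | Risk group: k, power | Center: k, power |
|---|---|---|---|
| 1:2 | 0 | 1.0034, 90.2% | 0.9935, 89.6% |
| 1:2 | 0.5 | 1.0073, 90.4% | 1.0041, 90.2% |
| 1:3 | 0 | 1.0120, 90.7% | 0.9950, 89.7% |
| 1:3 | 0.5 | 1.0106, 90.6% | 1.0065, 90.4% |
| 1:2:3:4 | 0 | 1.0120, 90.7% | 0.9931, 89.6% |
| 1:2:3:4 | 0.5 | 1.0101, 90.6% | 1.0063, 90.4% |
| 1:2:4:8 (extreme) | 0 | 1.0265, 91.4% | 0.9941, 89.7% |
| 1:2:4:8 (extreme) | 0.5 | 1.0258, 91.4% | 1.0056, 90.3% |

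Risk-group stratification adds 0.2 to 0.7 points in the moderate rows and 1.4 in the extreme one. A separate simulation of entry category alone, at about 1,600 events, gave 0.1 to 0.3 points. Since required events scale with k², the moderate range is worth 1,600 × (1.0034² − 1) ≈ 11 to 1,600 × (1.0120² − 1) ≈ 39 events.

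**4. Adding country.** At about 1,600 events, country by entry category gave 0.6 to 1.1 points if country log-rates have SD 0.3 to 0.5, and essentially no loss if countries do not differ. A second simulation (about 1,500 events, 42 assumed countries, SD 0.4 to 0.6, CHD-equivalent hazard ratio 2 to 2.5) moved mean Z from −3.12 to −3.15 and from −3.00 to −3.07. So k = 1.0096 and 1.0233, or about 90.5% and 91.3% from a 90% base, using rounded Z values.

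**5. Cost in information.** In that second simulation the log-rank variance was 377.1 unstratified, 375.8 by country and entry category (375.8/377.1 = 0.997, a 0.3% loss) and 372.7 by center (372.7/377.1 = 0.988, a 1.2% loss). Centers are small: 17,000/600 ≈ 28 patients and 1,600/600 ≈ 2.7 events each.

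**6. Validity.** Under no effect, five scenarios of 1,500 trials gave unstratified rejection rates of 6.2, 4.1, 5.6, 3.9 and 4.9%, averaging 4.9%. The stratified tests behaved the same within simulation error (standard error about 0.6 points per scenario).

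**The case against.** The strongest case against is that nothing here is wrong. A plain log-rank test is valid after center-stratified randomization, shows no type I error inflation, matches the pooled Kaplan-Meier curves planned beside it, and reaches the planned power. It also needs no pooling rules. All of that stands, and it limits the point to an efficiency suggestion.

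It is also fair that the size rests on assumptions. The protocol gives neither the mix of entry categories nor their event rates. The CHD-equivalent group includes type 2 diabetes alone (section 7.2, item e), so it is itself mixed, and if most patients enter that way the stratum separates little. The move of the hazard ratio toward 1 under pooling is the difference between a marginal and a conditional ratio and does not bias the test. Finally, section 13.1 leaves room for strata to be set in the statistical analysis plan, so the protocol's silence is not an omission.

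A reader might go further and infer that because randomization is stratified by center while the test is not, the mismatch costs power or validity. The figures do not support that. With about 2.7 events per center, stratifying by center changes power by −0.4 to +0.4 points. The strata proposed here are also not the randomization factor: country only coarsens center, and entry category plays no part in allocation.

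What survives is that a coarse prognostic stratum, available at no data cost, improves the test slightly in every scenario run.

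**Conclusion.** The test in section 13.7.1.2.3 is sound and, for a constant hazard ratio of 0.85, delivers the power in section 13.2. It can be improved slightly by using baseline risk information that the trial already holds. The expected gain is about 0.1 to 0.7 power points from the risk-group stratum and up to about 1 point with country added. Larger figures need extreme risk gradients or a country spread at the top of the assumed range. The direction is well supported; the size depends on assumed group shares, hazard ratios between groups and country spread. The difference between the randomization factor and the test is not the source of any loss. This is an optional, minor improvement.

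**What to change.** Reword the sentence in section 13.7.1.2.3 so that the primary analysis is a two-sided log-rank test stratified by entry category as recorded at baseline (CHD risk equivalent yes or no). Optionally add country, with small countries pooled by region under a rule fixed before unblinding. Do not stratify by center. Report the hazard ratio and 95% CI from a Cox model with the same strata, and keep the unstratified log-rank test as a sensitivity analysis. Section 13.7.2.2 then carries the change to the secondary composite and all-cause mortality.

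The cost is one sentence and no new data; section 13.1 allows revision on blinded review before data lock. There are two downsides: a pooling rule to prespecify if country is used, and a reported hazard ratio that is conditional on the strata and so does not correspond exactly to the pooled Kaplan-Meier curves.

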13.7.1.2.4 Multiple comparisons/multiplicity

If the primary efficacy reaches statistical significance, then the two secondary endpoints will be formally tested at the 5% level in a hierarchical (step-down) procedure. First the MI, stroke, cardiovascular death or hospitalization endpoint will be tested, and then, if this reaches significance, the all-cause mortality endpoint will be tested.

13.7.1.2.5 Other analyses for primary variable(s)

In order to further investigate the primary endpoint the following analysis will be done:

Subgroup analysis: The incidence of the primary efficacy endpoint will be summarized by a number of covariates including age, gender, and race to examine their potential effects. Each of these factors will be analyzed statistically using a Cox proportional hazards model incorporating terms for treatment, the covariate and the treatment-by covariate interaction. The number of patients with outcomes, estimated hazard ratios, and associated 95% confidence intervals will be calculated within each of the subgroups generated by these analyses.

13.7.2 Secondary/other efficacy variables

13.7.2.1 Description of secondary/other variables

- Secondary endpoint: The composite cluster of the first occurrence, over the duration of study (randomization to study end date inclusive), of the following cluster of events:
 - Any MI,
 - Any stroke
 - Cardiovascular death
 - Hospitalization for cardiovascular cause (unstable angina, transient ischemic attack, cardiac rhythm disorder, congestive heart failure, syncope, or urgent revascularization procedure)

- Other efficacy endpoints:
 - All-cause mortality

 - The following events taken separately will also be assessed:
 - Any MI
 - Any stroke
 - Cardiovascular death
 - Hospitalization for cardiovascular cause (unstable angina, transient ischemic attack, cardiac rhythm disorder, congestive heart failure, syncope, or urgent revascularization procedure).

 - The change from baseline measurement for waist circumference and weight will be assessed.

13.7.2.2 Statistical analysis of secondary/other variables

The secondary and other endpoints will be analyzed using the same statistical methodology as for the primary efficacy endpoint (except for weight and waist circumference).

13.8 Safety analysis

For this morbidity/mortality trial, a benefit risk assessment is important. For this purpose safety analyses will be conducted on the same population (ITT) and using the same evaluation period as for efficacy analyses. (ie, from randomization until study end date)

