11.2 Follow-up procedures after withdrawal

Patients who prematurely discontinue study drug are not to be replaced.

All randomized patients must be followed up according to the study flowchart until study end date or death, regardless of whether they discontinued study drug prematurely or not. Any event occurring after early study drug discontinuation will be recorded up through the study end date.

In case of study drug discontinuation (temporary or permanent) due to an adverse event, such patients will be closely monitored until the resolution or stabilization of this adverse event. This may mean that follow-up will continue after the patients have completed the study follow-up. Although data on that adverse event will continue to be captured, even

beyond the last visit, for new efficacy or safety events, only those that occur up through the last visit should be recorded.

In case of written withdrawal of consent (WOC) for follow-up visits, and unless otherwise stated by the patient in the informed consent form, Investigators will be encouraged to get information from the general practitioner, any other physician, or other medical-care provider, in order to follow the medical status of the patients (especially when they withdraw their consent after having experienced an AE/SAE or an efficacy endpoint). Investigators will also be expected to try as much as possible to re-contact those patients at the end of the trial, in order to obtain at least their vital status (dead or alive), as well as their stroke or MI status if possible, and thus avoid lost to follow-up for the efficacy assessment.

For patients considered lost to follow-up, the CRF must be completed up to the last visit performed.

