13.4 Data analysis considerations

13.4.1 Dataset analyzed

13.4.1.1 Treatment group considered for statistical analysis

For all efficacy and safety analyses, patients will be included in the treatment group to which they were originally allocated by the IVRS.

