13.4.1.2 Populations to be analyzed

The intent-to-treat (ITT) population will be used for all efficacy and safety analyses. This will consist of all randomized patients irrespective of whether the patient actually received study drug or the patient's compliance with the study protocol, in the treatment group assigned by the IVRS system. A patient will be considered randomized as soon as a treatment kit number is assigned by IVRS.

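### Adverse events and SAEs are analysed only by ITT to the study end date; with no on-treatment analysis beside it, relative measures of on-drug harm are diluted

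*Protocol*

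**What the plan says.** Section 13.4.1.2 of the protocol states: "The intent-to-treat (ITT) population will be used for all efficacy and safety analyses". That population takes in every randomized patient, "irrespective of whether the patient actually received study drug". Section 13.4.1.1 fixes the comparison groups: "For all efficacy and safety analyses, patients will be included in the treatment group to which they were originally allocated by the IVRS".

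Section 13.8 adds the time frame: "safety analyses will be conducted on the same population (ITT) and using the same evaluation period as for efficacy analyses". It gives benefit-risk assessment as the reason. Section 11.2 supplies the data for this: "Any event occurring after early study drug discontinuation will be recorded up through the study end date".

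Sections 13.8.1.1 to 13.8.1.4 plan numbers and percentages of patients with AEs, SAEs and AEs leading to discontinuation, each patient counted once per term. They define no treatment-emergent or on-treatment window. Section 13.8.2, and 13.8.3 by reference, limit laboratory and vital-sign summaries to patients with a test after the first dose, but abnormalities count at any time after randomization.

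The planning assumption that matters here is in Section 13.2: "These computations allow for a 10% annual rate of treatment discontinuation".

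**The concern.** In a superiority trial, off-drug follow-up pulls the treatment comparison toward no difference. For efficacy that is conservative. For harm the same pull works the other way: an effect present only while the drug is taken is measured over time that includes months or years without it. The relative excess then looks smaller, and an uncommon on-drug harm is harder to tell from chance.

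This is a stated rule and not a detail left open, because 13.4.1.2 and 13.8 positively assign ITT and the full study period to all safety analyses. The benefit-risk reason in 13.8 supports having an ITT safety analysis. It does not explain why that should be the only AE and SAE analysis.

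**Working it through.** **Inputs from the protocol (Section 13.2).** "Assuming recruitment over a 17 month period, and a total study duration of 50 months, 8,500 patients per group (total 17,000"); 10% annual treatment discontinuation; "3% is considered a reasonable assumption for the yearly event rate in the placebo group"; 15% risk reduction, two-sided 5% level, 90% power, about 1,600 events.

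**Assumptions not in the documents.** Uniform accrual; exponential and permanent stopping at the same rate in both arms, independent of the AE; AE hazard back to background at once after stopping; the AE rates and ratios below; any discontinuation rate other than 10%.

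**1. The plan's own figure.** Events needed = 4(1.960 + 1.282)² / (ln 0.85)² ≈ 1,592, or 1,599 by Freedman's formula. Expected events with 8,500 per arm and 33 to 50 months of follow-up are 1,577 (3% read as an annual probability) or 1,554 (3% read as a hazard). The stated 1,600 reproduces, so the accrual and follow-up frame can be used.

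**2. Share of follow-up on drug.** Follow-up T is uniform on 33 to 50 months, with mean 41.5 months = 3.458 years. With stopping hazard μ, on-drug share f = mean[(1 − e^(−μT))/μ] / 3.458.
- 10% as a hazard (μ = 0.10): 2.918 / 3.458 = 0.844.
- 10% as an annual probability (μ = −ln 0.9 = 0.105): 2.892 / 3.458 = 0.836.

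So about 16% of follow-up is off drug, and 29% to 30% of patients are off drug at the end of their own follow-up.

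**3. Diluted ratio** = 1 + (RR − 1) × f.

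| On-drug ratio | f = 0.844 | f = 0.836 |
|---|---|---|
| 1.5 | 1.42 | 1.42 |
| 2.0 | 1.84 | 1.84 |
| 3.0 | 2.69 | 2.67 |

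At an assumed 20% per year, f = 0.719 (hazard) or 0.694 (annual probability), so 28% to 31% of the relative excess is lost. Over an assumed 5% to 25% annual probability, 8.5% to 36.9% of time is off drug and a ratio of 2.0 appears as 1.92 to 1.63.

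**4. Power for an uncommon AE.** Assume 0.2% per year on placebo and an on-drug ratio of 1.5, with f = 0.844. Person-years per arm = 8,500 × 3.458 = 29,396. Power = Φ(ln RR / √(1/a + 1/b) − 1.96), where a and b are the expected events.
- ITT: 58.8 vs 83.6 events, ratio 1.42; 0.352/0.170 = 2.07; power 0.54.
- On treatment: 49.6 vs 74.4 events, ratio 1.50; 0.405/0.183 = 2.21; power 0.60.
- At 20% per year (hazard): 0.43 under ITT, 0.53 on treatment.

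The on-treatment comparison has more power despite fewer events.

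**5. Absolute excess.** In step 4 it is 83.6 − 58.8 = 24.8 events under ITT and 74.4 − 49.6 = 24.8 on treatment. A check on cumulative proportions agrees. At an assumed 0.3% per year, ratio 1.5 and 10% stopping, ITT gives 1.03% vs 1.46% and on treatment 0.86% vs 1.29%: a difference of 0.43 percentage points both times, with power 71% and 77%.

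**6. Common AEs.** At an assumed 1% per year and ratio 1.5, power is 99.5% under ITT and 99.8% on treatment, so little is lost.

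**The case against.** A reader might infer that the ITT rule shrinks the treatment difference in the very tables used to weigh benefit against risk. The documents do not support that. Section 13.8.1.2 plans crude counts and percentages and names no ratio or test for AEs. On-drug events stay in those counts, and off-drug time adds similar background events to both arms, so the absolute excess is unchanged (step 5). The power figures therefore describe a comparison a reader would make, not a test that 13.8 specifies.

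A reader might also infer that the rule masks neurological and psychiatric harm in particular. The protocol collects these events with scripted questions, but nowhere says that they occur mainly on drug or cause stopping. That premise is not used here.

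Other points stand in part:
- It is too broad to say that no safety table is tied to treatment. Laboratory and vital-sign summaries need a post-dose test, and AEs leading to discontinuation have their own table (13.8.1.4). Neither is an on-treatment analysis of AEs.
- Sections 11.1 and 11.3 ask for every attempt to restart drug, so the off-drug share may be below 16%. On the other hand, 11.1 names an adverse event as a justified reason to stop, so it could be higher in the active arm.
- On-treatment comparisons are open to informative stopping and miss late events. ITT handles both better, and 13.8 gives a sound reason for it. This defeats any proposal to make on-treatment the main analysis, but not one to show it alongside.
- The SAP, which is not at hand, could add such a table, and 13.1 allows revision. As written, however, the protocol assigns ITT to all safety analyses.

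**Conclusion.** The point holds as a moderate one that is cheap to remedy. The protocol fixes ITT to the study end date as the only AE and SAE analysis. At its own 10% discontinuation rate this removes about 16% of the relative excess of a harm confined to time on drug, and costs about six points of power in the 0.2% per year example. The loss grows with discontinuation and is negligible for common AEs. It falls on relative measures and power, not on the absolute risk difference.

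The size rests on harm that fades at once after stopping, on permanent stopping unrelated to the AE, and on the assumed AE rates. Delayed or persistent harm is not diluted and is better captured by ITT. The documents do not support the stronger conclusion that the ITT safety analysis is wrong or should be demoted.

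**What to change.** Keep the ITT analysis in 13.8 as the benefit-risk analysis. Add a co-reported on-treatment analysis of AEs, SAEs and laboratory abnormalities:

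- **Population:** patients who took at least one dose.
- **Period:** first dose to last dose plus a window whose length is fixed and justified before unblinding. The protocol gives no basis for a particular length, so none is suggested here.
- **Interruptions:** a rule for which time and events count when drug is stopped and restarted. Sections 8.10 and 13.6.1.2 already define a discontinuation as at least five consecutive days without intake.
- **Presentation:** exposure-adjusted rates by arm, next to the ITT counts, with a note that stopping may be informative.

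Reword 13.4.1.2 so that ITT is no longer the only safety population.

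Cost: a second set of safety tables and an edit to the statistical text, which 13.1 permits on blinded review before data lock. No new visits or data are needed, since AE onset dates (10.1) and treatment duration with patient-years on drug (13.6.1.1) are already planned. The drawback is that the added comparison is subject to informative stopping and misses events after the window. It should therefore supplement ITT and not replace it.
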